6. PHARMACEUTICAL INFORMATION

6.1 Study Agent (IND , NCI, Division of Cancer Prevention)

ENX Gel

(E/Z)-ENX ([E/Z]-4-hydroxy-N-desmethyltamoxifen hydrochloride), a 1:1 racemic mixture, is provided as a 0.5% (w/v, 5 mg/mL) and a 1.0% (w/v, 10 mg/mL) hydroalcoholic gel. Gel excipients include 60% ethanol, 1.5% (w/v) hydroxypropyl cellulose (Klucel HF), and 0.5% oleic acid in phosphate buffer at pH 7.0. The gel is provided in a pump with each pump action expelling 1 mL of gel containing 5 or 10 mg of ENX from the 0.5% and 1.0% mixtures, respectively.

Placebo Gel

Matching placebo gel contains the same excipients and is provided in the same pump format.

6.2 Reported Adverse Events and Potential Risks

(E/Z)-ENX gel, a 1:1 racemic mixture, is being provided in a topical hydroalcoholic gel for transdermal administration to the breasts for localized treatment. (Z) ENX is a highly active metabolite of tamoxifen, ~100 times more active, and thus this and another closely-related metabolite (Z) 4-hydroxytamoxifen (4 OHT) are thought to provide the bulk of tamoxifen's pharmacological activity. Consequently, tamoxifen is now viewed as a prodrug. ENX is formed in two steps from tamoxifen, by cytochrome P450 (CYP) 3A4 and CYP2D6, and then conjugated by phase II enzymes in the liver to inactive forms by sulfation or

glucuronidation [39]. Interconversion of (Z) - to (E)-ENX isoforms occurs spontaneously and bidirectionally in an aqueous environment, including media and biological fluids, though oxidative conditions and elevated temperatures increase isomerization [40]. (E) isomers of 4-OHT and ENX have much lower binding affinities for the estrogen receptor (ER) compared with their (Z) isomer versions, ~200 times lower affinity; thus, even in the presence of equal amounts of (E)-ENX, (Z)-ENX antagonism dominates ER pharmacological activity[41].

This protocol will be the first to treat women with topical doses of ENX gel in the US. However, women have previously been exposed to systemic ENX from oral tamoxifen dosing as a secondary consequence of its metabolism and from oral (Z)-ENX, an investigational breast cancer agent under evaluation by NCI, Division of Cancer Treatment and Diagnosis (DCTD). For the latter, in NCI-sponsored studies (NCT01327781, NCT01273168, and NCT02311933) women with ER-positive breast cancer are being treated with oral (Z)-ENX capsules, to avoid the metabolic requirement of CYP2D6 for tamoxifen since some women have CYP2D6 mutant alleles and thus are genotypically unable to properly or efficiently metabolize tamoxifen to its more active metabolites [42]. The human safety profile of oral (Z)-ENX capsules from the DCTD IND is summarized below, though topical dosing of ENX gel is anticipated to result in much lower systemic ENX so adverse events (AEs) may be significantly fewer and of lower grade. To support topical human dosing of ENX gel, animal toxicology studies have been completed and are described below. Finally, topical dosing of the closely-related molecule 4-OHT in a hydroalcoholic gel has been conducted in women for various different indications such as breast cancer [15, 36] and mastalgia (breast pain) [43]. These studies revealed that topical 4 OHT gel was well-tolerated though some transient and mild skin AEs occurred such as erythema and pruritis; topical ENX gel may exhibit a similar safety profile.

Oral (Z)-ENX - Human Safety Profile

Under the DCTD IND, which is cross-referenced by NCI, DCP's IND, women with metastatic breast cancer have been treated with capsules of oral (Z)-ENX. The dose escalation study did not identify a maximum tolerated dose (MTD) due to low toxicity of the agent and instead dose escalation was stopped at 160 mg/day since this dose achieved the target plasma steady-state concentration (Css) of >4 μM (Z)-pENX. Anti-tumor activity has been observed (data cut-off date 09/30/2014), with six partial responses in 55 evaluable patients. Common AEs in order of frequency have been (data cut-off date 09/30/2014): hot flashes (43%), lymphocyte count decreased (20%), anemia (19%), fatigue (17%), nausea (14%), platelet count decreased (13%), alanine aminotransferase increased (ALT, 12%), aspartate aminotransferase increased (AST, 12%), irritability (12%), white blood cell count decreased (12%), edema limb (10%), hypertriglyceridemia (10%), anorexia (9%), and high cholesterol (9%). Severe AEs were: ALT (grade 3), hypertriglyceridemia (grade 4), and thromboembolic events (one each grade 3 and 4).

Topical (E/Z)-ENX - Nonclinical Safety Profile << Final results pending ongoing studies>>

ENX has undergone preclinical animal testing sponsored by NCI, DCP and DCTD to support human clinical studies. These studies include multiple routes of administration to fully understand the systemic and local toxicity profiles. 28-Day toxicology studies of oral ENX or single-isomer (Z)-ENX have been completed in rats and dogs. A 28-day dermal toxicity study of ENX applied to mammary glands is underway in minipigs (results pending). ENX is not phototoxic based on a negative in vitro neutral red study. Finally, an immunotoxicity study, dermal delayed hypersensitivity, is underway in guinea pigs (results pending).

Oral (Z)-ENX doses ≤200 mg/kg/day were well-tolerated when administered for four days to female rats. Oral (Z)-ENX administered daily to rats for 28 days resulted in lethality at doses ≥80 mg/kg/day (≥480 mg/m2/day). The MTD was 20 mg/kg/day (120 mg/m2/day). Clinical signs of toxicity (abdominal

distention, dyspnea, hunched posture, and discharge from the nose/mouth) occurred mainly in rats administered \geq 80 mg/kg/day. Changes in clinical pathology parameters were noted in alkaline phosphatase (ALP), albumin, ALT, AST, calcium, and total protein; decreased uterine weight also occurred. Liver, lung, heart, kidney, gastrointestinal (GI), skeletal muscle, and reproductive tract toxicity were dose-limiting. With the exception of ovarian cysts and histiocytic infiltration of the lung, oral (Z)-ENX toxicity appeared to be reversible after a 28-day recovery period.

Oral 28-day dosing of rats with the racemic (E/Z)-ENX mixture at lower doses, 1, 20, or 40 mg/kg/day vs. single isomer (Z)-ENX at 40 mg/kg/day resulted in reduced body weight gain and/or body weight loss in males and females at all levels of treatment, though no definitive, dose-related alterations in clinical pathology parameters or clinical observations were noted. No definitive macro- or microscopic pathology observations occurred in male rats at any dose level, while the ovary was identified as a target organ in females following doses of 20 and 40 mg/kg/day (E/Z)-ENX and of 40 mg/kg/day (Z)-ENX. Microscopic pathology findings indicated that ovarian toxicity had not reversed 15 days following cessation of dosing.

Oral (Z)-ENX at 30 mg/kg/day resulted in dose-limiting emesis in female dogs after 4 consecutive days during a 28-day cycle. Reproductive tract toxicity was observed in females (vaginal epithelium hyperplasia) and males (atrophy of the prostate and testes, depletion of spermatozoa in the epididymides) and thymic atrophy in both sexes. Reproductive tract lesions were not reversible after a 28-day recovery period. A no observed adverse effect level (NOAEL) was not established. The MTD was >30 mg/kg/day (>600 mg/m2/day). With respect to body surface area, the MTD in dogs (>600 mg/m2/day) was at least five-fold greater than the rat MTD (120 mg/m2/day).

ENX dose-dependently inhibited human potassium channels in a patch-clamp study with a 50% inhibitory concentration (IC50) of 1.6 \square M which was similar to the IC50 value of 1.2 μ M for tamoxifen which is known cause adverse cardiovascular effects such as QT prolongation and torsades de pointes [44].

Topical (E/Z)-4-Hydroxytamoxifen - Human Safety Profile

Due to its similarity to ENX gel, the human safety profile of topical 4-OHT gel may be a guide for AEs. Topical 4-OHT in alcohol solution or gel has been administered to >450 pre- and postmenopausal women. In phase 1 safety and PK studies, topical 4-OHT was provided to women at doses ranging from 0.25–1 mg/breast/day for three weeks up to three months. Topical 4-OHT was well tolerated with only drug-related mild pruritus being observed in a few patients. Topical 4 OHT resulted in substantial breast tissue uptake with minimal metabolism and very low systemic plasma concentrations.

Phase 2 studies of topical 4-OHT up to 4 mg/day for up to six months was well-tolerated, absorbed, and pharmacologically active in breasts for reducing breast pain (mastalgia), breast density (a breast cancer risk factor), and breast cancer cell proliferation in women with ductal carcinoma in situ (DCIS) and locally advanced breast cancer. In a placebo-controlled, six-month phase 2 study of 4-OHT topical gel in premenopausal women with cyclical breast pain, the most common AEs seen in 4-OHT- vs. placebo-treated women (4 mg/day) were: headache (20% vs. 10%), nasopharyngitis (11% vs. 12%), application site reaction (4% vs. 0%), and pharyngitis (4% vs. 0% [36]. These events were all mild to moderate and some headaches and application site reactions (application site burning, itching) were deemed drug-related. Additional drug-related AEs seen in 4-OHT-treated women were decreased appetite, exfoliative dermatitis, and hypotension. No significant changes in hematologic parameters, liver function, renal function, electrolytes, or serum glucose were observed.

In a NCI, DCP-sponsored presurgical study of women with DCIS, 6–10 weeks of topical 4-OHT gel at 4 mg/day (2 mg to each breast) or oral tamoxifen at 20 mg/day resulted in similar 4-OHT breast levels and similar reductions in breast tumor cell proliferation [36]. Systemic levels of 4 OHT were markedly lower

(five-fold) with topical 4-OHT gel compared with oral tamoxifen. 4-OHT topical gel was well-tolerated and the most common AEs that were either similar or less frequent in 4-OHT- vs. tamoxifen-treated women were: hot flush (50% vs. 50%), breast pain (42% vs. 64%), fatigue (33% vs. 29%), and hyperhidrosis (25% vs. 43%). Only three AEs were elevated in 4-OHT-treated women compared with tamoxifen-treated women: pruritis (17% vs. 0%), vulvovaginal dryness (17% vs. 0%), and weight increased (17% vs. 0%).

6.3 Availability

Topical (E/Z)-ENX gel, 0.5% and 1.0%, an investigational agent, and matching placebo gel are supplied to investigators by NCI, DCP.

6.4 Agent Distribution

Agents will only be released by NCI, DCP after documentation of IRB approval of the DCP-approved protocol and consent is provided to DCP and the collection of all Essential Documents is complete (see DCP website for description of Essential Documents).

NCI, DCP-supplied agents may be requested by the Investigator (or their authorized designees) at each Organization. DCP guidelines require that the agent be shipped directly to the institution or site where the agent will be prepared and administered. DCP does not permit the transfer of agents between institutions (unless prior approval from DCP is obtained). DCP does not automatically ship agents; the site must make a request. Agents are requested by completing the DCP Clinical Drug Request form (NIH-986) (to include complete shipping contact information) and faxing or mailing the form to the DCP agent repository contractor:

[name] MRIGlobal DCP Repository [name] [contact]

[contact]

Emergency [contact]

6.5 Agent Accountability

The Investigator, or a responsible party designated by the Investigator, must maintain a careful record of the inventory and disposition of all agents received from DCP using the NCI Drug Accountability Record Form (DARF). The Investigator is required to maintain adequate records of receipt, dispensing and final disposition of study agent. This responsibility has been delegated to each accrual site's pharmacy. Include on receipt record from whom the agent was received and to whom study agent was shipped, date, quantity and batch or lot number. On dispensing record, note quantities and dates study agent was dispensed to and returned by each participant.

6.6 Packaging and Labeling

Topical (E/Z)-ENX gel, 0.5% and 1.0%, and matching placebo gel will be packaged by NCI, DCP.

6.7 Storage

In each institutional research pharmacy, the gel must be stored in a locked and secure area at room temperature, $59-86 \,^{\circ} \, F$ (15-30 $^{\circ} \, C$) and protect from light and moisture. Participants will be instructed to store their study agent in a location not accessible by children, at room temperature, and protected from light and moisture.

6.8 Registration/Randomization

- 1. A study coordinator must upload into the Northwestern Clinical Trials Management System, a signed and complete informed consent along with HIPAA authorization and a completed eligibility form for each participant identified as eligible to be entered into the study.
- 2. All participants must be registered in the Northwestern University Robert H. Lurie Comprehensive Cancer Center Clinical Trials Management System (CTMS). Participants must not start protocol treatment prior to registration in the Lurie Cancer Center CTMS.
- 3. After registration in the CTMS, participants will be assigned a participant identification number and a randomization number when applicable.
- 4. An NCPC Quality Assurance Monitor will submit the following into the REDCap Randomization Information Form: (1) Study Number, (2) Site, (3) Pharmacist Email(s), (4) Participant ID [PID], (5) Participant Initials, and (6) Randomization Date.
- 5. An Automatic Treatment Assignment Notification email will be sent to the research pharmacist(s) containing: (1) Study Number, (2) Site, (3) Participant ID [PID], (4) Participant Initials, (5) Randomization Date, and (6) Treatment Assignment.
- 6. The clinical research coordinator(s) will receive a Confirmation of Registration containing the PID via email.
- 7. The following people will have a copy of the un-blinded randomization log: the study statistician at NU, the Quality Assurance Team at NU, and the Investigational Pharmacists at each site. The following people will have access to the REDCap study project containing randomization information: the study statistician at NU and the Quality Assurance Team at NU. The study statistician will set up randomization blocks.

When possible, the study coordinator will notify an NCPC Quality Assurance Monitor and/or send an email to [contact] prior to registering a participant. Prior notification is required for participant randomizations outside the normal business hours of Monday-Friday 9:00am-5:00pm CT.

6.9 Blinding and Unblinding Methods

Study participants will receive a prescription, blinded, from the investigational pharmacy. The blind will be maintained through the effort of the pharmacodynamics analyst and the pharmacy. Unblinding will occur when it is deemed medically necessary or in the event of a DLT and will only take place after consultation with the NCI, DCP Medical Monitor:

Name: [name]

Address: Division of Cancer Prevention

National Cancer Institute

[name]

[name]

[contact] (during normal business hours)

[contact] [contact]

Email: [contact]

After hours consultation will be provided by [name], at [contact] or [contact].

6.10 Agent Destruction/Disposal

DCP-supplied agents: at the completion of investigation, all unused study agent will be returned to NCI, DCP Repository according to the DCP "Guidelines for AGENT RETURNS" and using the DCP form "Return Drug List".

7. CLINICAL EVALUATIONS AND PROCEDURES

7.1 Schedule of Events

SCHEDULE OF EVENTS

Procedure	Screening Visit 1 ¹	Day 8±3, 15±3, 22±3 (1st day of study drug =day 1)	Study Visit 1 (day before surgery) ⁶	Study Visit 2 Day 22 to 29 (day of surgery) ⁸	Study Visit 3 Day 29-50 (7- 14 days after surgery)	Phone, email, or text Follow-Up Day 60 ±7
Assess Eligibility	X					
Informed Consent	X					
Registration	X					
Randomization	X					
Medical History	X			X ⁷		
ECOG Performance Status	X					
Last Menstrual Period	X		X		X	X
Physical Exam	X			X^7		
Vital Signs/ Height and Weight	X			X	X	
Body Mass Index	X					
Breast cup size	X					
Breast skin photos	X		X^9		X^{10}	
BESS Questionnaire	X		X			
Tobacco and Alcohol Use Questionnaires	X		X			
CTCAE skin toxicity	X	X	X		X	
Clinical Labs (LFTs and Renal function tests)	X			X		
Urine or Serum Pregnancy Test	X^2			X ⁵		
Research blood specimen collection	X			X		
Tissue procurement for research purposes ³	X			X		
Concomitant Medications	X	X	X		X	
Dispense Study Agent and diary ⁴	X					
Collect Study Agent			X			

Procedure	Screening Visit 1 ¹	Day 8±3, 15±3, 22±3 (1st day of study drug =day 1)	Study Visit 1 (day before surgery) ⁶	Study Visit 2 Day 22 to 29 (day of surgery) ⁸	Study Visit 3 Day 29-50 (7- 14 days after surgery)	Phone, email, or text Follow-Up Day 60 ±7
Review Agent			X			
Diary/Record						
Adverse Events		X	X		X	
assessment						
Telephone/Email		X				X
Contact						

¹Screen 1 will occur within 6 weeks prior to registration.

7.2 Baseline Testing/Pre-study Evaluation

7.2.1 Screening Visit 1

The following will be collected:

- 1. Informed Consent
- 2. Medical History per treating physician
- 3. ECOG performance status
- 4. Prior and concomitant medication review
- 5. Vital signs assessment
- 6. Physical Exam per treating physician within 6 weeks of registration
- 7. Clinical labs for renal and hepatic function including total bilirubin, AST, ALT, alkaline phosphatase, blood urea nitrogen, and creatinine to be collected within 6 weeks prior to registration
- 8. Blood collection for research purposes:
 - a. Two 3 mL Blue Top tube (citrate) for coagulation panel.
 - b. Two 10mL Lavender top tubes (K₂EDTA) to obtain plasma for hormone level measurement (estradiol, progesterone, and androgens [DHEA (dehydroepiandrosterone),

²Required within 5 days prior to starting study treatment for females of child-bearing potential. Women of child-bearing potential whose Screening Visit 1 occurs >5 days prior to starting study agent, will have a separate office visit to conduct a second pregnancy test within 5 days of starting study agent.

³Tissue will be obtained from the diagnostic core needle biopsy (DCNB) as well as the surgical resection specimen for study end points. Though there is no physical collection of tissue at Screening Visit 1, release for acquisition of DCNB tissue will be completed at this visit.

⁴Participants who are unable to pick up the study medication will receive it via mail or courier delivery requiring signature to confirm receipt.

⁵Urine or serum pregnancy test is routinely performed for females of child-bearing potential prior to the surgery.

⁶Study Visits 1 and 2 may be combined on the same day if feasible and convenient (i.e. surgery start time allows completion of Study Visit 1 tasks prior to surgery start time). If this is not possible, Study Visit 1 will occur on the day prior to surgery.

⁷Source document will be anesthesiologist or surgeon pre-op history and physical. May have been performed on day of surgery or within 28 days prior.

⁸Participants who require a delay in surgery will be allowed to continue treatment for up to 7 additional days.

⁹ Study Visit 1 skin photos will be taken only in participant experiencing skin toxicity, and will focus on the area showing the skin toxicity.

¹⁰ Study Visit 3 skin photos will be taken only in participants who had documented skin toxicity at Study Visit 1, and will focus on the area showing the skin toxicity.

androstenedione, and testosterone]) and measurement of IGF-1, IGFBP-3, and SHBG. Buffy coat (white blood cells (WBC)) will be saved for DNA/RNA isolation for future pooled analyses if the subject consents to this optional study.

- 9. Skin symptoms per CTCAE criteria (Table 1)
- 10. Review of conformance with Inclusion / Exclusion criteria
- 11. BESS questionnaire (Appendix D)
- 12. Tobacco and Alcohol Use Questionnaires
- 13. Breast skin photos
- 14. Breast cup size
- 15. Body Mass Index (BMI)
- 16. Collection of last menstrual period date for premenopausal participants
- 17. Urine or serum pregnancy test for women with child-bearing potential
- 18. Registration and randomization
- 19. Dispensing study medication (for participants who are not able to pick it up, the study medication will be delivered via mail or courier requiring signature for confirmation of receipt). Participants of child-bearing potential will begin dosing within 5 days of a negative pregnancy test.
- 20. Participant diary (Appendix B and C) will be reviewed and dispensed along with the study medication.
- 21. Tissue will be obtained from the DCNB as well as the surgical resection specimen for study end points. Though there is no physical collection of tissue at Screening Visit 1, release for acquisition of DCNB tissue will be completed at this visit.

The amount of study agent that will be distributed to the participant at the screening visit will be 1 canister of active or placebo gel. They will return it at Study Visit 1 (the evening before or the morning of surgery).

7.3 Evaluation During Study Intervention

7.3.1 Weekly phone calls for monitoring of toxicity and compliance. (Days 8 ± 3 , 15 ± 3 , 22 ± 3) All participants will be followed during intervention via weekly telephone calls by the clinical research staff to assess compliance and adverse events. The study staff will call on days 8, 15, 22 from the first day of study medication (±3 days). If these days are non-business days, the calls will be made on the next closest business day. Emails may be substituted for the weekly phone calls. Please refer to Appendix E for suggested statements for participant communications.

At these phone calls, the following with be collected:

- 1. Concomitant medication review
- 2. Adverse events To assess adverse events participants will be asked non-leading questions, followed by the questions in Appendix E as needed, to document if they have experienced any of the following symptoms:
 - a. Skin symptoms based on Table 1, explained to participants using plain language
 - b. Hot flashes
 - c. Vaginal discharge
 - d. Uterine spotting/ Uterine bleeding
- 3. Additionally, any other symptom experienced by participants will be recorded to assess adverse events.
- 7.3.2 Study staff will also call participants four days prior to surgery to remind participants to continue study agent for the last three days prior to surgery. If a reminder call falls on a non-business day, the call will be made on the next closest business day. Reminder calls may be substituted for emails and may be combined with weekly phone calls for monitoring toxicity and compliance.

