3. SUMMARY OF STUDY PLAN

3.1 In this double-blind, randomized Phase I trial, a maximum of 38 participants who are planning mastectomy (unilateral or bilateral, for therapy or risk-reduction) will be accrued into each of three cohorts. The study agent is transdermal ENX gel versus placebo gel applied to the breast skin, starting with 10 mg ENX gel daily and proceeding to 20 mg daily (5 mg and 10 mg to each breast at each dose level). The ENX gel and placebo gels contain 60% (v/v) or 47.4% (w/v) alcoholic solution with 0.5% (v/v) or 0.45% (w/v) oleic acid. The trial will be conducted in the pre-surgical window setting, enrolling women who need unilateral or bilateral mastectomy, with a treatment period consisting of a 28 days \pm 7 days, leading up to the day of mastectomy. Accrual will occur at NWU, MSKCC, and at Cedars Sinai Los Angeles (CS-LA).

- 3.2.1 We planned a 2:1 (ENX:placebo) randomization in cohort 1 and cohort 2, while all cohort 3 subjects would receive active gel at the final dose, but would cease therapy 3 days prior to surgery. Of the twelve Cohort 1 subjects, eight received ENX gel 10 mg daily (5 mg per breast) and four received placebo. Since no subject experienced dose-limiting toxicity (DLT) in Cohort 1, we proceeded to Cohort 2, where 12 subjects again were randomized 2:1. Eight received ENX gel 20 mg daily (10 mg per breast), and four received placebo gel. We initially planned that if no more than one subject experiences DLT, we would proceed to Cohort 3, where eight subjects would receive ENX gel at 20 mg daily (10 mg per breast), but stop gel application 3 days prior to surgery. An interim analysis was conducted after completion of Cohort 2 and discussed on April 13, 2020. Although only one subject in Cohort 2 experienced DLT, we observed more skin irritation in Cohort 2 participants. There was no permeation advantage with the higher dosage. Therefore, we decided to use a 10 mg daily dose for Cohort 3. Since drug concentration in the breasts was variable in the interim analysis, all Cohort 3 subjects will continue daily application of study drug until the day prior to surgery, in order to better assess the drug distribution in the breast. We expect a total of 8 subjects will complete Cohort 3, therefore a total of 32 subjects will complete the study.

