5.1 Dose Regimen and Dose Groups

This is a Phase 1 trial with a 2:1 randomization to active or placebo ENX gel applied to the breast skin, bilaterally. The study agent and placebo will be supplied by National Cancer Institute, Division of Cancer Prevention (NCI-DCP) and will be dispensed in metered canisters that deliver 1 ml of gel per pump (see more detail in 2.2 study agent). Briefly, ENX gel products with study agent were manufactured to deliver 5 mg or 10 mg of ENX mixture (E/Z=50:50) in 1mL (= 0.8985 g) of gel per pump. Therefore, one pump will deliver each dose 5 mg or 10 mg of (E/Z) ENX per breast. Considering the application to both breasts, the final daily gel doses will be 10 mg or 20 mg of ENX gel. In Cohort 1, active gel subjects will apply 10 mg ENX gel daily (5 mg gel in 1 pump to each breast) and in Cohort 2 active gel subjects will apply 20 mg ENX gel daily (10 mg in 1 pump to each breast). The last day of study agent administration will be the day before surgery. In Cohort 3, there is no randomization, all 8 subjects will apply10 mg ENX gel daily (5 mg gel in 1 pump to each breast) until the day before surgery. Skin health of the breasts will be established at baseline, and skin toxicity will be monitored weekly through phone calls, and at the

end of intervention through physical examination, and documented by photographs. Subjects with active skin disease on the breast (psoriasis or eczema) are excluded, as are those with ulcerated cancers. Subjects will be advised to not expose breast skin to direct sun or tanning beds, to not shower/bathe for at least 4 hours following gel application, and to avoid contact of breast skin with other individuals for at least 4 hours after application. After 4 hours, if contact is likely, the breast may be cleansed with a washcloth, or by bathing/showering.

The duration of intervention is 21-28 days. If required, because of a delay in surgery, up to extra 7 days of treatment will be allowed.

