5.2 Study Agent Administration

- 5.2.1 All participants will receive either active gel or placebo gel each day and will be blinded to their randomization status. The study gel will be self-administered. All subjects in Cohort 3 will receive active drug.
- 5.2.2 One 90 ml canister of gel products containing placebo or study agent will be distributed to each participant at the baseline visit. Each participant will apply the gel daily to both breasts for 21-28 days. One pump (1 mL) of placebo or active gel products will be applied to both breasts once a day. The last day of gel application will be the day prior to the day of surgery.
- 5.2.3 The gel (ENX/placebo) should be applied in the morning after daily shower (in order to minimize potential transfer to the partner at night). Participants will be instructed on application of the drug to the breasts during the initial study visit, and will apply it each morning after a shower, allow it to dry for one minute and dress as usual. If they forget to apply the gel in the morning, administration later in the day is acceptable, as long as the skin has been washed since the last application. If a dose is missed and applied late, 12 hours should elapse before application of the next dose. Participants will be instructed not to bathe, swim, or shower for at least 4 hours after gel application. Contact of other individuals with the treated breasts is unlikely to be associated with significant transfer of drug; contact is permitted after the treated area has been washed with soap and water and washing is allowable after a minimum of 4 hours post-application.
- 5.2.4 The day of surgery, participants should refrain from applying any study agent, and be sure to bathe, shower, or wash their breasts before coming to surgery, to avoid the possibility of recently applied gel contaminating the samples taken for drug assays.

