For Reminder Phone Calls four days prior to surgery, please use the following suggested statement.

"Hello my name is [insert name] from [site name/department], regarding NWU2017-09-01 TopEND research study. This message is for [insert name]. Please remember to continue applying your study agent for the last 3 days prior to surgery and complete your participant diary. Your last gel application should be on the day before your surgery. If you have any questions please call [insert name], Research Coordinator at (xxx) xxx-xxx."

For the Last Phone Call to premenopausal women, please use the following suggested statement:

"Hello my name is [insert name] from [site name/department], regarding NWU2017-09-01 TopEND research study. Is this a good time to talk?"

If no: "When would be a better time for me to call you?"

If yes: "Have you had a period since we last met? If so, what was the start date?"

"Thank you for your time and for participating in this study."

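### Toxicity monitoring is stated to be weekly during intervention, but calls are listed only to day 22 (±3) while gel may run to day 35, leaving a nominal 13-day gap for the most delayed surgery

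*Combined protocol and SAP*

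**What the plan says.** Section 7.3.1 gives the general rule: "All participants will be followed during intervention via weekly telephone calls by the clinical research staff to assess compliance and adverse events". Section 5.1 says the same of skin toxicity, the schema lists weekly calls for compliance and adverse events, and section 3.5.1 names the weekly calls among the time points for the primary endpoint.

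The contacts themselves are enumerated. Section 7.3.1 says "The study staff will call on days 8, 15, 22 from the first day of study medication", within ±3 days, and the Schedule of Events has one column for them, headed "Day 8±3, 15±3, 22±3 (1st day of study drug =day 1". The next column with skin grading is Study Visit 1.

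On treatment length, section 5.1 says "The duration of intervention is 21-28 days" and then "If required, because of a delay in surgery, up to extra 7 days of treatment will be allowed". Section 3.1 gives 28 ± 7 days "leading up to the day of mastectomy". Section 5.2.2 fixes the end point: "The last day of gel application will be the day prior to the day of surgery".

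Section 7.3.2 adds a call or email four days before surgery. Its stated purpose is adherence, and it may be merged with a weekly call. The suggested Appendix E text reads in part "Please remember to continue applying your study agent for the last 3 days prior to surgery and complete your participant diary" and asks nothing about skin or symptoms, unlike the weekly script in the same appendix.

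**The concern.** The stated frequency and the enumerated days agree for the standard 21-28 day course but part company in the extension. Staff who work from the list would make no prompted toxicity contact between about day 22 and Study Visit 1, which can fall on day 35 or 36.

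Dermal tolerability is the primary endpoint (section 8.1). A dose-limiting toxicity requires a Grade 2 or greater reaction lasting at least 48 hours at the application site (sections 3.2.2 and 13.7), so onset and duration have to be captured. Section 5.6 discontinues agent at such an event, which can happen only once the event is known. A reaction that begins and settles after the last call, and that the woman does not report, would be dated and graded from memory at Visit 1. Under section 7.4.1, photographs at that visit are taken only if toxicity is then present (section 3.5.2 does not state that limit, but a photograph of healed skin would not show the event).

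The groups are small, so single events count. One event among the 8 women of Cohort 3 is 1/8 = 12.5 percentage points of incidence. If Cohorts 1 and 3 are pooled at 10 mg, which section 13.4 leaves open, it is 1/16 = 6.25 points.

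**Working it through.** **Inputs.** Day 1 is the first gel day (Schedule of Events). With D gel days, the last application is on day D and surgery on day D + 1 (section 5.2.2). D is 21-28, or at most 28 + 7 = 35 (section 5.1). Study Visit 1 is on day D, or on day D + 1 if combined with surgery (section 7.4). The last listed call is on day 22 ± 3, that is, days 19-25.

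**Check against the plan's own figures.**
- Study Visit 2, stated as day 22 to 29: 21 + 1 = 22 and 28 + 1 = 29. Reproduced.
- Study Visit 3, stated as day 29-50 and 7-14 days after surgery: 22 + 7 = 29 and (35 + 1) + 14 = 50. Reproduced.
- Without the extension, the upper limit of Visit 3 would be 29 + 14 = 43. The Visit 3 window therefore allows for surgery on day 36, while the call list was not extended to match.

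**Gap from last call to Study Visit 1.** Nominal gap = visit day − 22; range = visit day − 25 to visit day − 19.

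| Gel days D | Visit 1 on day D: nominal (range) | Visit 1 on day D + 1: nominal (range) |
|---|---|---|
| 28 | 6 (3-9) | 7 (4-10) |
| 29 | 7 (4-10) | 8 (5-11) |
| 30 | 8 (5-11) | 9 (6-12) |
| 35 | 13 (10-16) | 14 (11-17) |

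With Visit 1 the day before surgery, the nominal gap first exceeds 7 days at D = 30, which only the extension permits.

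**Days strictly between contacts, D = 35, Visit 1 on day 35.** After a call on day 25: days 26-34, 9 days, 9/35 = 26%. After a call on day 19: days 20-34, 15 days, 15/35 = 43%.

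**The reminder.** 36 − 4 = day 32. No listed weekly call is near enough to merge with it. If it were counted as a toxicity contact, the gap before it would be 32 − 22 = 10 days nominally (7-13), followed by 3 days to Visit 1.

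**Like-for-like comparison.** Consecutive listed calls are nominally 7 days apart, but the windows alone allow (15 + 3) − (8 − 3) = 13 days. The fair comparisons are 13 against 7 at nominal timing, and 16 against 13 at the window extremes.

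**The case against.** The strongest reply is that this is an incomplete list rather than a flat contradiction. The weekly statement is general, the three days fit the standard course, and the extension enters the schedule only by footnote, so a sensible coordinator would keep calling weekly. That reading is reasonable, and the gap arises only if the list is taken as exhaustive. But the Schedule of Events is what sites follow, and nothing in it or in 7.3.1 says that the calls continue.

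A reader might infer that women in the extension are unmonitored. The documents do not support that. Section 3.5.1 provides for reactions reported between visits: photograph upload, CTCAE grading, and a consultation, where judged necessary or requested, within 48 hours (72 over a weekend). Visit 1 still assesses adverse events and grades the skin. What is missing is a prompted contact.

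A reader might also divide the gap by treatment length and conclude that 10-16 of 35 days (29-46%) lack assessment. Day 35 is itself an assessment day, so the figure is 9-15 days (26-43%). Nor should 16 days be set against 7, since that compares a window extreme with a nominal interval.

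Finally, it is tempting to say that follow-up is thinnest at the very end of exposure. The last four gel days of a 35-day course contain both the reminder (day 32) and Visit 1 (day 35). The Appendix E texts are only suggested, so staff may ask about symptoms at the reminder, though nothing requires it.

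**Conclusion.** The point holds, with limited reach. As listed, the schedule leaves a nominal 13 days between toxicity contacts (10-16; 11-17 if Visits 1 and 2 are combined) for a woman treated 35 days, although the plan states weekly follow-up during intervention. The consequence is possible late detection, and recall-based onset and duration, of a primary-endpoint event while gel continues.

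This rests on three assumptions: the day list is followed as written, the full 7-day extension is used after 28 days, and the reminder is run from its suggested script. With a shorter extension the gap shrinks, and at 28 gel days it is 6 days nominally. The documents do not say how many surgeries are delayed. Cohorts 1 and 2 are complete, so a change now reaches mainly the 8 planned Cohort 3 women, and among them only those whose treatment runs past about 29 days. It cannot alter the placebo-controlled data already collected.

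**What to change.** Reconcile the call list in 7.3.1 and the Schedule of Events with the protocol's own weekly statement and its own allowed treatment length, so that the listed contacts cover the whole time gel is applied. Use the existing Appendix E skin and symptom questions at the existing pre-surgery reminder. Neither step touches dose, treatment duration or the toxicity rules.

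As an illustration, with a contact at day 29 ± 3 the nominal gaps for a 35-day course become 29 − 22 = 7 days and 35 − 29 = 6 days (7 if Visit 1 is on day 36). The windows would still allow 32 − 19 = 13 days between the last two calls, and questions at the day-32 reminder would not shorten that. The gain is therefore a prompted contact in the extension rather than guaranteed weekly spacing.

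The cost is about one extra call or email per affected woman (7.3.1 already accepts email) and a few lines of script, with no added visit.
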